#### 4.5. Dose Justification

An investigational medicinal product (IMP) will not be administered to subjects enrolled in this study.

#### Radiation Exposure

The total radiation exposure **for the pSS subjects** who are subjected to the studies with  $^{18}\text{F}$ -FDG and  $^{11}\text{C}$ -MET including its associated low-dose CT scans is expected to be **9.7mSv**, below 10mSv which falls within the Group IIb, intermediate risk category as per the International Commission of Radiological Protection (ICRP) and generally considered ethically acceptable also for healthy volunteers *ie* 5.2mSv for the  $^{18}\text{F}$ -FDG and associated CT, and 4.5mSv for the  $^{11}\text{C}$ -MET components.

**The healthy volunteers** undergoing PET/CT will only receive  $^{11}\text{C}$ -MET with its associated low-dose CT scans and hence be exposed to **4.5mSv**.

The average yearly radiation exposure from naturally occurring background radiation in the United Kingdom (UK) is 2.3mSv. Approval will also be obtained from the UK Administration of Radioactive substances Advisory Committee (ARSAC) prior to commencement of the study.

#### 4.6. Benefit:Risk Assessment

The following section outlines the risk assessment and mitigation strategy for this protocol:

#### 4.6.1. Risk Assessment

Potential Risk of Clinical Significance	Summary of Data/Rationale for Risk	Mitigation Strategy
Study Procedures		
Minor salivary gland biopsy (Group B only)	This procedure is associated with (a low) incidence of complications including discomfort, bleeding and haematoma formation.	
Subject selection:
 
 
• Subjects with bleeding disorders will be excluded from the study (exclusion # 4).
 
• Subjects with an abnormal clotting screen or low platelet counts will be excluded from the study (exclusion #21).
 
• Subjects who are unable to discontinue anti-coagulant medication to allow biopsy will be excluded(exclusion #16).
 
 
Subject management
 
 
• Local anaesthetic will be administered to reduce discomfort.
 
• The biopsy will be performed by qualified physicians, surgeons or dentists with appropriate training and experience in the procedure
 

Subject exposed to ionizing radiation	
Radiation exposure from PET/CT scanning:
 
Radiation exposure from PET/CT scanning comes from two sources: the radionuclide injected for PET scanning, and the exposure to X-rays from the CT component. The estimated radiation doses for the whole study are 9.7mSv for pSS subjects and 4.5mSv for healthy volunteers. A typical diagnostic whole body CT scan would result in an exposure of around 10-15mSv.
	
Study design:
 
 
1. Low dose CT will be employed to minimize radiation exposure.
 
2. Subject age is restricted to <math>\geq 40</math> years for healthy volunteers and <math>\geq 30</math> years for pSS subjects to restrict radiation exposure for younger subjects (inclusion #1 and #4).
 
3. In stream data reviews will be performed to minimize the number of scans
 

Potential Risk of Clinical Significance	Summary of Data/Rationale for Risk	Mitigation Strategy
	
An exposure of 9.7mSv approximates to 4 years of background radiation in the United Kingdom, and the additional risk of developing a fatal malignancy as a result of an exposure of 9.7mSv for the pSS subjects has been estimated as approximately 1 in 2100 for an adult in normal health. For healthy volunteers the total maximum effective dose of 4.5mSv is equivalent to approximately 2 times the average yearly exposure to background radiation and the additional risk of developing a fatal malignancy as a result of these exposures has been estimated at 1 in 4400 for an adult in normal health [ICRP, 2007]. To put this into context, in developed countries, the overall population risk of dying of cancer is 1 in 5 for females and 1 in 4 for males. Exposures of less than 10mSv are generally considered acceptable for research in healthy volunteers (for discussion of potential foetal toxicity see separate section below).
	
involving ionizing radiation that will be conducted

Potential radiation exposure to foetus of pregnant subject
	
Ionizing radiation from CT scans and PET tracers The potential risks of concern from foetal exposure to ionizing radiation are non-cancer adverse effects (eg miscarriage, malformation), and risks of childhood cancer. If for any reason a pregnant subject is
	
Study design:
 
 
• Pregnant females are not eligible for the study (inclusion # 9).
 
• Female subjects considering the study will be advised about the need to avoid pregnancy during the study until Follow up, and about the contraceptive and pregnancy testing requirements of the
 

Potential Risk of Clinical Significance	Summary of Data/Rationale for Risk	Mitigation Strategy
	
scanned, radiation exposure to the foetus from the whole study would be in the order of 10mGy or less for the pSS subjects, and lower for healthy volunteers. No non-cancer foetal adverse effects of radiation exposure (eg miscarriage, foetal malformation) have been detected below 50mGy exposure.
 
For a foetus exposed in utero to 10mGy of radiation, the absolute risk of cancer at ages 0-15 years of age is about 1 excess cancer death per 1700 exposed (Annals of the ICRP, Volume 30, 1, 2000 (ICRP, 2000)).
	
study before consent.
 
 
Females of reproductive potential will be required to use highly effective methods of contraception (as specified in the protocol) for 28 days prior to Visit 1 until Follow up.
 
 
Subject monitoring and management:
 
 
Females of reproductive potential will undergo pregnancy testing to exclude pregnancy prior to scanning as described in inclusion #9.
 
 
Withdrawal criteria:
 
In the event of a pregnancy in a female subject in the study, the subject will be withdrawn.

Subject exposed to gadolinium containing MRI contrast agents
	
The study uses DOTAREM (gadoterate meglumine) as an MRI contrast agent.
 
Non clinical data (source: gadoterate meglumine Summary of Product Characteristics (SPC))
 
The recommended clinical dose is 0.1mmol/kg (ie 0.2mL/kg). The administration of DOTAREM in rats and in dogs at daily doses up to 3mL/kg (ie 15 times the dose laid down in clinical conditions) and for 28 days cause no other effect than a reversible vacuolisation of the proximal tubular cells of the kidney.
	
Subject selection:
 
 
Subjects with impaired renal function (estimated glomerular filtration rate [eGFR] <60 mL/minute/1.73m^2) are excluded by the eligibility criteria (exclusion #20).
 
Subjects with a history of sensitivity to gadoterate meglumine containing contrast agents will be excluded from the study (exclusion #18).
 
 
The site(s) will be responsible for following any additional safety guidelines for the specific gadoterate meglumine containing contrast agent used at the site and not scan

Potential Risk of Clinical Significance	Summary of Data/Rationale for Risk	Mitigation Strategy
	
Preclinical studies have demonstrated that DOTAREM is non-toxic for gestating females, non embryo-toxic and non teratogenic for the foetus. No prior peri- and post-natal toxicity and fertility studies have been carried out (source: SPC).
 
Clinical data: Use of MRI contrast agents in subjects with severely impaired renal function [Glomerular Filtration Rate (GFR) <30mL/minute has been associated with Nephrogenic Systemic Fibrosis (NSF)] (this is a class risk rather than specific for this particular agent). In subjects with severely impaired renal function, the benefits of the use of contrast agents should be carefully weighed against the risks.
 
Gadolinium (Gd) contrast agents can be associated with anaphylactoid or hypersensitivity or other idiosyncratic reactions, characterized by cardiovascular respiratory or cutaneous manifestations, and ranging to severe reactions including shock. The risk of hypersensitivity reactions may be higher in case of previous history of reactions, bronchial asthma and history of allergic disorders. Most of these reactions occur within half an hour of administration. Delayed reactions (after hours or several days) have been rarely
	
subjects if contra-indicated(exclusion #19). Subject monitoring and management
 
 
• The MRI procedure will be conducted under the supervision of trained and qualified clinical staff who are trained to appropriately manage an allergic reaction.
 
• MRI contrast at a dose less than or equal to 0.1mmol/kg will be used. If it is necessary for technical reasons to repeat the MRI (no more than once), gadolinium contrast administration will not be repeated within a 24 hour period.
 
 
For pregnancy risk mitigations please see section above (potential radiation exposure to foetus of pregnant subject).

Potential Risk of Clinical Significance	Summary of Data/Rationale for Risk	Mitigation Strategy
	observed	
Subject exposed to a high field MRI magnet	Certain prostheses or foreign bodies might be incompatible with the MRI scanner	
Subject selection: All participants will be screened according to local scanner criteria and trial inclusion/exclusion before entering the MRI room to ensure they are able to have the MRI conducted. Subjects with non-MR compatible metal implants or implantable electronic devices (eg pacemaker, defibrillator) will not be included in the study (exclusion #8).

Administration of PET tracers $^{18}\text{F}$ -FDG and $^{11}\text{C}$ -METHionine (including potential risks to a fetus of a pregnant subject)	
<math>^{18}\text{F}</math>-FDG PET Tracer: Nonclinical data: Toxicological studies with a single intravenous (IV) injection of <math>^{18}\text{F}</math>-FDG at 50-fold human dose in dogs and 1000-fold human dose in mice have not identified potential risks of clinical significance.
 
<math>^{11}\text{C}</math>-MET PET tracer Methionine is an essential amino acid that is not synthesized de novo in humans, who must ingest methionine or methionine containing proteins. The daily adult requirement of methionine is 10mg/kg [Protein and amino acid requirements in human nutrition. Report of a joint Food and Agriculture Organization of the United Nations (FAO)/ World Health Organisation (WHO)/ United Nations University (UNU) expert consultation [WHO, 2007]. The dose
	
Study design:
 
 
• The <math>^{11}\text{C}</math>-MET will be produced according to Good Manufacturing Practice (GMP), and the specifications in the European Union (EU) Pharmacopoeia.
 
• <math>^{18}\text{F}</math>-FDG is purchased from a commercial producer, in accordance with product labelling.
 
• The radiotracers will be administered at doses according to product labelling (where available) and the EU Pharmacopoeia.
 
• Staff handling the tracers will have the necessary training and authorizations in their use.
 
• For pregnancy risk mitigations please see section above (potential radiation exposure to foetus of pregnant subject).
 

Potential Risk of Clinical Significance	Summary of Data/Rationale for Risk	Mitigation Strategy
	administered is several hundred fold less than the recommended daily intake of this essential amino acid. It is not anticipated that there will be any risks (reproductive or other) of the molecule itself (excluding ionizing radiation), although no foetal reproductive toxicity data is available	

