### 5. SELECTION OF STUDY POPULATION AND WITHDRAWAL CRITERIA

Deviations from inclusion and exclusion criteria are not allowed because they can potentially jeopardize the scientific integrity of the study, regulatory acceptability or subject safety. Therefore, adherence to the criteria as specified in the protocol is essential.

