#### CONCURRENT CONDITIONS/MEDICAL HISTORY (INCLUDES LIVER FUNCTION AND QTc INTERVAL)

1. Diagnosis of secondary Sjögren's Syndrome.
2. Diagnosis of another systemic autoimmune disease, apart from pSS, including but not limited to, systemic lupus erythematosus, rheumatoid arthritis, systemic sclerosis or systemic vasculitis. For Group B subjects, autoimmune conditions associated with pSS (for example autoimmune thyroiditis, primary biliary cirrhosis or coeliac disease), are not included in this exclusion, but should be described in the medical history taken baseline. If in doubt please consult the medical monitor.
3. Subjects with active life-threatening or organ-threatening effects of pSS meaning that they may not be able to complete the study visits according to the protocol (as determine by the investigator) (Group B).
4. History of coagulation or bleeding disorders which would increase the risk of minor salivary gland biopsy (for example but not limited to Haemophilia A or B, Von Willibrand's disease, platelet function disorders) (Group B).
5. History of malignancy within 5 years of screening that, in the view of the investigator, in consultation with the medical monitor if required, could confound the results of the F-FDG PET/CT scan (including lymphoma associated with pSS). This does not include cervical carcinoma in situ or non-melanoma skin malignancy that has been treated with curative surgical treatment.
6. History of unresolved acute or chronic infection that, in the view of the investigator in consultation with the medial monitor, if required, could confound the results of the F-FDG PET/CT.
7. Subject has diabetes mellitus requiring insulin therapy.
8. Contraindications to MRI scanning (as assessed by MRI safety questionnaire).

9. History of, or suffers from, claustrophobia or feel that they will be unable to lie still in the PET or MRI scanner for a period of up to 1 to 2 hours.
10. Where participation in the study would result in donation of blood or blood products in excess of 500mL within a 56 day period.

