#### CONCOMITANT MEDICATIONS

14. Group A: healthy volunteers. Subject is unable to refrain from taking prescription or non-prescription drugs (including vitamins and dietary or herbal supplements), within 7 days prior to Visit 1 until completion of Visit 2, unless in the opinion of the investigator and Sponsor the medication will not interfere with the study.
15. Group B- pSS subjects taking immunomodulatory treatment at screening are excluded unless they have been on stable doses of these medicines for 6 weeks prior to Screening/Baseline and are expected to remain on stable doses of these medications until the Follow up visit. This would include drugs such as glucocorticoids, immunosuppressive agents (for example hydroxychloroquine, azathioprine, methotrexate, mycophenolate mofetil, and biologic therapies). Permitted medications are listed in Section 6.8. If in doubt please discuss with the Medical Monitor.
16. Group B: pSS subjects. Receiving treatment with anti-coagulant medications, including but not limited to warfarin, heparin, thrombin inhibitors, and Factor Xa inhibitors, and aspirin, unless the subjects is able to discontinue these medications one week prior to minor salivary gland biopsy, or according to local guidelines. The treatment may be restarted 3 days after the biopsy, or according to local guidelines.

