**DIAGNOSTIC ASSESSMENTS AND OTHER CRITERIA**

20. Estimated GFR [Modification of Diet in Renal Disease (MDRD) calculation] of less than 60mL/min/1.73m^2 at screening.
21. Platelet count below the laboratory normal range at screening, or prothrombin time above the laboratory normal range at screening (Group B).
22. Subject with a fasting blood sugar >11.1mmol/L at screening (defined as fasting for a minimum of 6 hours, excluding unflavoured water).

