**Full physical examination:** will include complete assessment of all organ systems including assessments of the head and neck (including eyes, ears, nose, throat, and thyroid gland), skin, musculoskeletal (including evaluation of both small and large joints), neurological, respiratory, and cardiovascular systems, gastrointestinal system and abdomen (including liver and spleen), lymph nodes and extremities.

**Urinalysis:** will be performed as related to the eligibility criteria listed in Section 5.1 and Section 5.2.

In addition, urinalysis will be performed in subjects included in Group B in order to calculate the ESSDAI score. If proteinuria is detected on dipstick ( $\geq$ trace), quantification of the spot urine protein:creatinine ratio will be needed in the laboratory to calculate the ESSDAI score.

**Haematology (including coagulation screen) and blood chemistry (clinical safety laboratory assessments):** will be performed as related to the eligibility criteria listed in Section 5.1 and Section 5.2.

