**Table 4 Protocol Required Safety Laboratory Assessments**

Laboratory Assessments	Parameters			
Haematology	Full blood count indices		Red blood cell count Indices:	White blood cell count with Differential:
	White blood count	Mean corpuscular volume (MCV)	Neutrophils	
	Platelet Count	Mean corpuscular haemoglobin	Lymphocytes	
	Haemoglobin	Mean corpuscular haemoglobin concentration	Monocytes	
	Haematocrit		Eosinophils	
	Coagulation screen		Basophils	
	Prothrombin time, Activated partial thromboplastin time			
Clinical Chemistry	Urea	Potassium	Aspartate aminotransferase	Total bilirubin
	Creatinine	Sodium	Alanine aminotransferase	Total Protein
	Glucose (fasting for 6 h [excluding unflavoured water])	Calcium	Alkaline phosphatase	Albumin
	Creatine kinase	C-reactive protein	Chloride (pSS patients only)	Bicarbonate (pSS patients only)
Routine Urinalysis	
 
• Specific gravity
 
• pH, glucose, protein, blood and ketones by dipstick
 
• Microscopic examination (if blood or protein is abnormal) and send urine for spot urinary protein:creatinine ratio
 
			
Other Screening Tests	
 
• Follicle-stimulating hormone and oestradiol (as needed in females of reproductive potential only)
 
• Serum human chorionic gonadotropin (hCG) [at screening only] and urine hCG pregnancy test (as needed for females of reproductive potential)
 
• Group B only: anti-Sjögren's-syndrome-related antigen A (Anti-SSa),
 
			

Laboratory Assessments	Parameters
	anti-Sjögren's syndrome type B (SSb), total immunoglobulin (Ig), IgG, IgA, IgM, serum protein electrophoresis, complement C3, C4, CH50 
 
• Optional additional tests in Group B (if needed for calculation of ESSDAI): cryoglobulins, urine electrophoresis, urinary protein creatinine ratio (if dipstick <math>\geq</math> trace protein).
 
• Estimated glomerular filtration rate will be calculated using the modification of diet in renal disease (MDRD) formula.
 

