## NOTES :

European League Against Rheumatism (EULAR) primary Sjögren's syndrome disease activity [ESSDAI]

Safety laboratory tests are only conducted at screening in this study. Subjects with values that are considered clinically significantly abnormal will be assessed according to the inclusion/exclusion criteria. In the event of clinically significant laboratory values the investigator will advise the subject of appropriate clinical care.

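### Section 4.6.1 says exclusion 21 keeps out subjects with an abnormal clotting screen, but exclusion 21 omits aPTT, so no written criterion excludes an isolated prolonged aPTT before the biopsy

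*Protocol*

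**What the plan says.** The risk table in Protocol Section 4.6.1 names discomfort, bleeding and haematoma as the complications of the minor salivary gland biopsy, which only Group B undergoes. Among the subject-selection safeguards it states: "Subjects with an abnormal clotting screen or low platelet counts will be excluded from the study (exclusion #21".

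Exclusion 21 in Section 5.2 reads: "Platelet count below the laboratory normal range at screening, or prothrombin time above the laboratory normal range at screening (Group B".

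Table 4 (Section 7.3.4) lists the coagulation screen as: "Prothrombin time, Activated partial thromboplastin time". Section 7.2.1 includes that screen among the screening tests done for eligibility, under the item "Haematology (including coagulation screen) and blood chemistry (clinical safety laboratory assessments".

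Two other exclusions bear on bleeding. Exclusion 4 covers "History of coagulation or bleeding disorders which would increase the risk of minor salivary gland biopsy". Exclusion 16 covers subjects "Receiving treatment with anti-coagulant medications, including but not limited to warfarin, heparin, thrombin inhibitors, and Factor Xa inhibitors, and aspirin", unless the drug can be stopped before the biopsy.

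On abnormal screening results, the notes to Table 4 say: "Subjects with values that are considered clinically significantly abnormal will be assessed according to the inclusion/exclusion criteria". Section 5 does not allow deviations from the criteria and adds: "Therefore, adherence to the criteria as specified in the protocol is essential".

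**The concern.** The risk table promises a rule and cites the criterion that is meant to carry it out. That criterion covers less than the promise. By the protocol's own definition, a clotting screen is abnormal if either prothrombin time or aPTT is abnormal, yet only prothrombin time leads to exclusion.

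A site following Section 5.2 could therefore enrol, and take a biopsy from, a subject whom the sponsor's risk assessment describes as excluded. Bleeding is a named risk of a procedure that brings the subject no direct medical benefit (Section 4.6.2). The benefit:risk conclusion in Section 4.6.3 rests on the listed mitigations. Safety laboratory tests are done only at screening, so this is the one planned clotting check before the biopsy.

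**Working it through.** The plan states no figure to reproduce, so the main check compares the texts.

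**Which tests does the risk-table sentence cover?** Low platelets, plus an abnormal clotting screen. By Table 4 the screen is prothrombin time and aPTT. That makes three tests.

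**Which of these does a written criterion enforce for Group B?**

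| Test or situation | Criterion | Leads to exclusion? |
|---|---|---|
| Platelets below normal range | Exclusion 21 | Yes |
| Prothrombin time above normal range | Exclusion 21 | Yes |
| aPTT above normal range | None | No |
| Known bleeding disorder that raises biopsy risk | Exclusion 4 | Yes, but on history, not on a screening result |
| Anticoagulant or aspirin use | Exclusion 16 | Yes, unless the drug can be stopped, and on medication, not on a screening result |

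**Does any other provision fill the gap?**

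- Inclusion 3 deals with laboratory abnormalities not otherwise listed, but it applies to Group A, who have no biopsy.
- Section 7.2.1 and the notes to Table 4 send abnormal results back to the eligibility criteria, none of which mentions aPTT.
- Section 7.7 on the biopsy adds no clotting check. It leaves technique and sample handling to the Study Reference Manual, which is not among the documents.
- Section 5.4 lets the investigator withdraw a subject for safety. This is permissive and is not an eligibility rule.

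A Group B subject with normal platelets, normal prothrombin time, no bleeding history, no anticoagulant and a prolonged aPTT therefore meets no listed exclusion.

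**Is this a leftover from the amendment?** No. The original protocol has the same mismatch. Amendment 1 revised this panel, removing thrombin time because it is not part of the standard coagulation screen, and kept aPTT.

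**How often might it arise?** The documents give no frequency of isolated aPTT prolongation, so the per-subject frequency p is an assumption. Group B has n = 8 to 12 (Section 4.3). The expected number is n × p, and the chance of at least one is 1 − (1 − p)^n.

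| Assumed p | n | Expected number | Chance of at least one |
|---|---|---|---|
| 1% | 8 | 8 × 0.01 = 0.08 | 1 − 0.99^8 = 7.7% |
| 1% | 12 | 12 × 0.01 = 0.12 | 1 − 0.99^12 = 11.4% |
| 2.5% | 8 | 8 × 0.025 = 0.20 | 1 − 0.975^8 = 18.3% |
| 2.5% | 12 | 12 × 0.025 = 0.30 | 1 − 0.975^12 = 26.2% |
| 5% | 8 | 8 × 0.05 = 0.40 | 1 − 0.95^8 = 33.7% |
| 5% | 12 | 12 × 0.05 = 0.60 | 1 − 0.95^12 = 46.0% |

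The 2.5% row is what would follow if the laboratory's range were a central 95% range. These figures show how often the rule would be called on. They do not measure bleeding.

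**The case against.** The strongest reply is that Section 4.6.1 is a summary, that it points to exclusion 21, and that exclusion 21 is clear and binding. Other entries in the table also paraphrase loosely. For example, it says that subjects with bleeding disorders are excluded, whereas exclusion 4 is limited to a history that would increase biopsy risk. On this reading the summary is imprecise and no exclusion is missing.

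The remaining gap is also narrow. Exclusions 4 and 16 catch known disorders and anticoagulant users. The aPTT result is available before the biopsy, the investigator must advise on care for clinically significant results and may withdraw the subject, and the operator must be trained. The Study Reference Manual may add pre-biopsy checks. Many results just outside a normal range carry no raised bleeding risk, so an automatic exclusion would cost some harmless screen failures in a group of 8 to 12.

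Much of this stands as a limit on the consequence. The impact is small, the frequencies are assumed, and the point establishes the lack of a written eligibility criterion, not the lack of any control.

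It does not remove the inconsistency. The risk table makes a definite statement that the subject will be excluded, and discretion to withdraw is weaker than that. If the table is only a loose summary, it overstates the protection on which the benefit:risk conclusion relies. If it is binding in its own right, it gives a site the opposite answer to Section 5.2 for the same subject. Either way the text needs correcting.

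**Conclusion.** The concern holds. The stated safeguard against biopsy bleeding is delivered for platelets and prothrombin time but not for aPTT: two of the three tests. An isolated prolonged aPTT first found at screening is excluded by no written criterion, and the outcome rests on investigator discretion.

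The textual finding depends on no outside figure. The estimate of how often it would matter depends wholly on the assumed 1% to 5% frequency. The practical safety impact is small, because the result is known before the biopsy and the protocol describes complications as infrequent. It should be corrected because the operative criterion does not do what the risk assessment says it does.

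**What to change.** Add to exclusion 21 (Group B): *or aPTT above the laboratory's normal range at screening*. This uses the same threshold as the existing prothrombin time rule and makes the criterion match the mitigation in Section 4.6.1.

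The cost is one line at the next amendment. aPTT is already measured at screening, so no new test is needed. The downside is an occasional extra screen failure: about 0.1 to 0.6 per 8 to 12 otherwise eligible subjects under the assumed 1% to 5% frequency.

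If the clinical team means platelets and prothrombin time to be the only gate, the alternative is to narrow Section 4.6.1 to those tests and state how an abnormal aPTT is handled before the biopsy. Narrowing the wording alone would remove the contradiction but leave the abnormal result without a rule.
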